12.6.3. Pharmacodynamic

PainCart Assessments		
General		

 For PainCart assessments, baseline is defined as the mean value of the two assessments taken prior to dosing in each session (Day 1). The following PainCart endpoints will be assessed utilising all available individual assessments recorded during the study periods (AAUC: Analysis area under the curve, PDT = pain detection threshold, PTT = pain tolerance threshold): 
 UVB Heat: PDT AAUC Cold Pressor: PDT, PTT AAUC Electrical stair (pre-cold pressor): PDT, PTT AAUC Electrical burst: PDT, PTT, AAUC Conditioned pain modulation (CPM): PDT, PTT AAUC The following PainCart endpoints will be assessed at Baseline, Day 1, Day 2, Day 8 and Day 15 (AAC: Area above the curve from eVAS, AUC = area under the curve from eVAS, PDT = pain detection threshold, PTT = pain tolerance threshold, (e)VAS = ((electronic) visual analogue scale)): 
 UVB Heat Pain Detection – Normal Skin Cold Pressor: PDT, PTT, post-test VAS Electrical stair (pre-cold pressor): PDT, PTT, post-test VAS Electrical stair (post-cold pressor): PDT, PTT, post-test VAS (for use in calculation for CPM) Electrical burst: PDT, PTT, AUC, post-test VAS Pressure Pain: PDT, PTT, AUC, post-test VAS The UVB heat pain endpoint on irradiated skin will be assessed at all timepoints mentioned above except for Day 15. 		
Conditioned Pain Modulation (CPM)		

 CPM is the activation of the pain-modulatory mechanism, as part of the descending endogenous analgesia system. The degree of CPM is assessed by comparing the electrical pain thresholds for the single stimulus paradigm before and after the cold pressor task. i.e. CPM = Post-Cold Pressor electrical stair threshold – Pre-Cold electrical stair threshold 		
Derivation of AAUC for PainCart Assessments		

 The following analysis AAUC's for the PainCart assessments will be calculated as follows: 		
Assessment	AAUC's Calculated	Derivation Details
Heat Pain Detection on UVB skin	AAUC (1-8 Days)	➤ Baseline = Day 1 (Pre-Dose)

PainCart Assessments					
Cold Pressor Detection and Tolerance	AAUC (1-15 Days)	➤ Baseline = Day 1 (Pre-Dose)			
All other PainCart assessments	AAUC (1-15 Days)	➤ Baseline = Day 1 (Pre-Dose)			

 The weighted mean AAUC parameters will be derived by calculating the area under the curve (AUC) using the trapezoidal rule, and then dividing by the actual relevant time interval (i.e. $t_f - t_l$): $\textbf{Weighted Mean AAUC}(t_f - t_l) = \frac{\frac{1}{2} \sum_{i=1}^{I-1} (t_{i+1} - t_i)(y_{i+1} + y_i)}{t_l - t_f}$ 
Where (example provided for UVB heat pain detection AUC(1-8 Days):
 
 y_i = Value of endpoint at i^{th} time point t_i = The i^{th} actual time point (days) for UVB heat pain detection: 
 t values will be calculated as the actual time recorded in the SAS dataset in the SAS datetime format. For baseline, the timepoint will be calculated as the midpoint of the two pre-dose assessments. t_f = Actual time point of first non-missing obs t_l = Actual time point of last non-missing obs I = Number of time points used in the AAUC calculation 					
Seeds for PainCart Analyses – PROC MCMC					

 Seeds for all planned analyses were determined in advance using the following SAS code (analysis_seed.SAS) and documented within this RAP prior to unblinding: <pre>data temp; do i = 1 to 15; number=round(100000*ranuni(0),1); output; end; run; proc print; run;</pre>					
Endpoint	Test	Analysis	Macro Seed		
Heat Pain	Detection	Mixed ANCOVA	57743		

PainCart Assessments			
Cold Pressor	Tolerance	Mixed ANCOVA	95933
	Detection	Mixed ANCOVA	55572
Electrical Pain – single stimulus (Pre-cold pressor)	Tolerance	Mixed ANCOVA	01749
	Detection	Mixed ANCOVA	19282
Conditioned Pain Modulation (CPM)	Detection	Mixed ANCOVA	46555
	Tolerance	Mixed ANCOVA	33042
Electrical Pain – repeated stimulus	Tolerance	Mixed ANCOVA	80088
	Detection	Mixed ANCOVA	73186

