4. ANALYSIS POPULATIONS

Population	Definition / Criteria	Analyses Evaluated
Screened	
 • All participants who were screened for eligibility 	
 • Study Population • Safety
Enrolled	
 • All participants who passed screening and entered the study. • Note screening failures (who never passed screening even if rescreened) and participants screened but never enrolled into the study (Reserve, Not Used) are excluded from the Enrolled population as they did not enter the study. 	
 • Study Population
Randomized	
 • All participants who were randomly assigned to treatment in the study. • This population will be based on the treatment sequence the participant was randomized to. 	
 • Study Population
Safety	
 • All randomized participants who received at least one dose of study treatment. • This population will be based on the treatment sequence the subject actually received. • Note: Participants who were not randomized but received at least one dose of study treatment should be included. 	
 • Safety • PK/PD
Pharmacokinetic (PK)	
 • All participants in the Safety population who had at least 1 non-missing serum PK assessment. • Note: Non-quantifiable [NQ] values will be considered as non-missing values 	
 • PK
Intent-To-Treat (ITT)	
 • All randomized participants who received at least one dose of study treatment. • This population will be based on the treatment sequence the subject was randomized to. • Any participants who receives a treatment randomization number will be considered to have been randomized. 	
 • PainCart • Study Population
Modified Intent-to-Treat (MITT)	
 • All randomized participants who received at least one dose of study treatment and completed at least one PainCart assessment in at least two study periods. • This population will be based on the treatment sequence the subject was randomized to. • Any participants who receives a treatment randomization number will be considered to have been randomized. 	
 • PainCart

Population	Definition / Criteria	Analyses Evaluated

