UVB Safety	
 Those in the Safety Population who also perform the UVB Heat Pain detection PainCart assessments on irradiated skin. 	
 Safety (UVB Sensitivity)
UVB Intent-to-Treat (UVB-ITT)	
 Those in the ITT Population who also perform at least one UVB Heat Pain detection PainCart assessment on irradiated skin in at least one study period. 	
 PainCart UVB heat pain irradiated skin endpoint - summary
UVB Modified Intent-to-Treat (UVB-MITT)	
 Those in the MITT Population who also perform at least one UVB Heat Pain detection PainCart assessment on irradiated skin in at least two study periods. 	
 PainCart UVB heat pain irradiated skin endpoint - analysis

Refer to [Appendix 12](#): List of Data Displays which details the population used for each display.

A populations exclusion meeting will be held before unblinding of the data. The meeting minutes and list of participants excluded from the populations mentioned in Section 4: Analysis Populations will be documented and uploaded to eTMF. A summary and listing of the participants excluded from certain populations will be created.

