7.1.4. Strategy for Intercurrent (Post-Randomisation) Events

Intercurrent current events (ICE) are defined as:

- Early withdrawal from study due to Covid-19
- Early withdrawal from study not due to Covid-19
- Use of prohibited medications
- Early discontinuation of study drug
- Use of COVID-19 vaccinations.

The “Hypothetical” strategy will be applied to handle the “Early withdrawal from study due to Covid-19”, “Early withdrawal from study not due to Covid-19 and “Early discontinuation of study drug” in the analysis for all endpoints. For the “Early withdrawal from study due to Covid-19” ICE, this strategy attempts to estimate treatment effects had the Covid-19 ICE not occurred. With COVID-19, the likelihood of participants withdrawing from the study is increasing (e.g. closure of the site, participants advised not

to leave homes etc.) which makes the Hypothetical strategy reasonable. The “Use of prohibited medications” and “Use of COVID-19 vaccinations” ICEs will implement a “Treatment Policy” strategy. The strategy implies direct use of data irrespective of the occurrence of the intercurrent events. The “Treatment policy” strategy is the same as de facto type estimand.

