7.1.5. Statistical Analyses / Methods

Details of the planned displays are provided in [Appendix 12](#): List of Data Displays and will be based on GSK data standards and statistical principles.

Unless otherwise specified, endpoints / variables defined in Section [7.1.1](#) will be summarised using descriptive statistics, graphically presented (where appropriate) and listed.

Table 2: Primary PainCart Analyses details which of the primary endpoints are to be analysed and/or summarised.

Table 2 Primary PainCart Analyses

Estimand	Endpoint	Summary*	Primary Analysis – Bayesian AAUC Mixed ANCOVA	Listing
UVB Heat Pain	Detection (UVB Skin)	Yes	Yes (AAUC 1-8 days)	Yes (Inc. AAUC)
Cold Pressor	Tolerance	Yes	Yes (AAUC 1-15 days)	Yes (Inc. AAUC and eVAS)
Electrical pain – single stimulus (Pre-Cold Pressor)	Tolerance	Yes	Yes (AAUC 1-15 days)	Yes (Inc. AAUC and eVAS)

*The summary will include summary statistics for the summary measures, AAUC and post-test eVAS scores.

MMRM: Mixed Model Repeated Measures; ANCOVA: Analysis of Covariance; AAUC: Analysis Area Under Curve, BRM: Bayesian Repeated Measures

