12.7.2. Handling of Missing Data

Element	Reporting Detail
General	
 • Missing data occurs when any requested data is not provided, leading to blank fields on the collection instrument: 
 ○ These data will be indicated by the use of a “blank” in subject listing displays. Unless all data for a specific visit are missing in which case the data is excluded from the table. ○ Answers such as “Not applicable” and “Not evaluable” are not considered to be missing data and should be displayed as such.
MMRM Analysis	
 • All the available assessments taken at scheduled visits will be included in the repeated measures models in which missing data are not explicitly imputed but the correlation between visits for all participants is used to adjust the estimate of treatment effect considering any missing data.

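### Does the primary AAUC need a minimum-coverage rule, so that periods ending at Day 2 are not analysed as AAUC(1-15) or AAUC(1-8)?

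*SAP*

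**What the plan says.** SAP 12.6.3 states that the AAUC endpoints "will be assessed utilising all available individual assessments recorded during the study periods". The trapezoidal area is divided by the time between the first and last non-missing observations. The endpoint of that interval is defined as "Actual time point of last non-missing obs", so it is not tied to Day 8 or Day 15. Baseline is itself a point on the curve: "For baseline, the timepoint will be calculated as the midpoint of the two pre-dose assessments".

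Table 2 in SAP 7.1.5 places these values in the column headed "Primary Analysis – Bayesian AAUC Mixed ANCOVA", as AAUC 1-8 days for UVB and 1-15 days for cold pressor and electrical pain. The entry conditions in SAP 4 name no study day. MITT requires that a participant "completed at least one PainCart assessment in at least two study periods"; UVB-MITT requires "at least one UVB Heat Pain detection PainCart assessment on irradiated skin in at least two study periods".

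For withdrawal, SAP 7.1.4 adopts a hypothetical strategy and says, of COVID-19 withdrawal, that "this strategy attempts to estimate treatment effects had the Covid-19 ICE not occurred". The only model-based missing-data text, in SAP 12.7.2, reads "All the available assessments taken at scheduled visits will be included in the repeated measures models in which missing data are not explicitly imputed".

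**The concern.** In a complete AAUC(1-15), the Day 8 and Day 15 tests carry about 71% of the weight. In a period that stops after Day 2 they carry none, yet the value has the same label and enters a model with one pooled residual variance. Under a hypothetical strategy, averaging only the observed hours targets the full-window effect only if that effect is roughly constant over the window.

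Nothing else in the SAP closes the gap. The 12.7.2 row describes repeated-measures models, and the primary model is an ANCOVA on a single summary per period. The Early Withdrawal visit has no PainCart test, so leaving the study does truncate the period. For irradiated skin, a missed Day 7 irradiation is enough to remove the Day 8 test. The sample is small and Protocol 9.2.1 plans for 20% dropout. If truncation were common and the effect changed over time, the primary estimate would be distorted.

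**Working it through.** **Plan's own figure.** 24 completers with 20% dropout: 24/(1 - 0.20) = 30, the stated maximum. For UVB, 15/0.80 = 18.75, against the stated approximate 18. The study stopped at the futility interim, so the check below uses 18 enrolled and 15 completers.

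**Trapezoid weights.** Test times are 1, 3, 24, 26, 168, 170, 336 and 338 h (Schedule of Activities). The baseline midpoint is assumed to be 2 h pre-dose.

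- Complete 1-15 period: 0.4, 0.7, 3.4, 3.4, 21.2, 21.2, 24.7, 24.7, 0.3%. Days 8 and 15 together carry 70.9%.
- Stopped at 26 h: 5.4, 8.9, 41.1, 41.1, 3.6%. The interval is (26 + 2)/24 = 1.17 days, or about 2.2 days if Day 2 is done 24 h late, as the SAP window allows.

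**Value of the AAUC** (log effect of 1 where present):

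| Time course | Complete 1-15 | Stopped at 26 h | Ends at Day 8 | Complete 1-8 |
|---|---|---|---|---|
| Target engagement (0.90 to Day 8, 0.75 at Day 15; Protocol 4.4) | 0.86 | 0.85 | 0.89 | 0.89 |
| Constant | 1.00 | 0.95 | 0.99 | 0.99 |
| Delayed (Day 8 onward) | 0.71 | 0 | 0.42 | 0.42 |
| Early only (to Day 2) | 0.29 | 0.95 | 0.57 | 0.57 |

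**How many periods.** Assume three dropouts, uniform over 28 + 28 + 15 = 71 days. A Period 1 dropout has one period only and is outside MITT. Affected periods are those of participants leaving between Day 2 and Day 8 of Period 2 or 3, a total of 12 days:

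- affected: 3 × 12/71 = 0.51
- analysed: 45 + 3 × (28 × 2 + 15 × 3)/71 = 49.3
- fraction: 0.51/49.3 = 1.03%

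With longer gaps between doses, or with 30 enrolled, the fraction is 0.7% to 1.3%.

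**Shift in the estimate** = fraction × (stopped/complete - 1). For AAUC(1-15) this gives -0.01% (target engagement), -0.05% (constant), -1.0% (delayed) and 1.03% × (0.946/0.287 - 1) = +2.4% (early only).

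**In standard errors.** Take the Table 1 cold pressor CV of 25.6% as within-subject. For the two planned sequences, SE = √(ln(1 + 0.256²) × 1.5/15) = 0.080. At an assumed whole-window ratio of 1.10, 0.024 × ln(1.10)/0.080 = 0.03 SE. This raises root-mean-square error by √(1 + 0.03²) - 1, which is under 0.05%.

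**Cost of excluding short periods.** Within-subject information per participant is 2/3 with three periods, 1/2 with two and 0 with one.

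- total: 15 × 2/3 + 3 × (28 × 1/2 + 15 × 2/3)/71 = 11.0
- lost: 3 × (6 × 1/2 + 6 × 1/6)/71 = 0.17, or 1.5%
- SE: 1/√(1 - 0.015) = 1.008, an increase of 0.8%

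**Extreme bound.** Put all three dropouts between Day 2 and Day 8 of Period 2. Then 3/51 = 5.9% of periods are affected. The early-only shift is 5.9% × 2.3 = 13.5%, or 0.16 SE, which adds 1.3% to root-mean-square error. Exclusion would lose 1.5/11.5 = 13% of the information, and 1/√(1 - 0.13) raises the SE by 7.2%.

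**What exclusion leaves behind.** Periods ending between Day 8 and Day 15 number 3 × 14/71 = 0.59, slightly more than the 0.51 removed. They still shift the estimate by 1.2% × (0.42/0.71 - 1) = -0.5% (delayed) or 1.2% × (0.57/0.29 - 1) = +1.2% (early only).

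**The case for a change.** The best case for a change is that this is the definition of the primary endpoint, the gap in the text is real, and one programming condition would close it. The human time course is unknown; Protocol 2.1 says the mechanism is not well understood, so a profile parallel to target engagement is an assumption. Missed visits without withdrawal are not in the frequency above. With 15 to 18 participants in two sequences, a single truncated period is a visible share of its treatment-by-period cell.

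The textual part stands. So does a limit on the arithmetic: the comparison depends on effect size. At a whole-window ratio of 1.30, early-only, the bound gives 0.135 × ln(1.30)/0.080 = 0.44 SE. That adds about 9.4%, more than the 7.2% cost of exclusion. But a whole-window ratio of 1.30 carried by Days 1 and 2 alone means a ratio of exp(ln(1.30)/0.287), about 2.5, on those days. No passage suggests this.

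The remedy is also not clearly nearer the stated strategy. Dropping a period discards valid Day 1 and Day 2 data and rests on its own missing-at-random assumption. Cutoffs at Day 8 or Day 15 and the present rule can each be defended.

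**Conclusion.** No change is needed. The SAP uses a time-normalised mean over the observed interval. This is an explicit convention, applied alike to both treatments, and with no drug effect it creates no treatment difference unless truncation is related to treatment or outcome. The expected distortion in AAUC(1-15) is between -1.0% and +2.4% of the effect and practically nil under target engagement. At a ratio of 1.10 it is at most about 0.03 SE, against an SE cost of 0.8% for the exclusion rule.

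Timing points the same way. RAP Amendment 1 follows the futility stop. SAP 3.1 lists Clinical Statistics and Clinical Programming among the functions unblinded to interim data, and the interim analysed the same AAUC measure. Changing which periods enter the primary model at that stage would weaken prespecification for no gain in accuracy.

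The remaining loose ends are ones analysts settle without instruction. The MMRM row in 12.7.2 is inapplicable text. A period with pre-dose values only has one time point, so its AAUC is undefined and can only be missing. SAP 12.5.2 already has the impact of major timing deviations assessed, and the PainCart listings, which include the AAUC, make short periods visible. A count of truncated periods or a restricted sensitivity run would be harmless but would not be expected to alter the conclusion.

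This rests on assumed uniform dropout, three dropouts among 18, nominal test times and the Table 1 CV. The actual number of truncated periods is not in the documents.

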12.6.4. Safety

Adverse Events

 Adverse events will be coded using the current MedDRA coding dictionary at the time of reporting providing a Preferred Term (PT) and a System Organ Class (SOC) for analysis and reporting.

ECG Parameters
RR Interval

 IF RR interval (msec) is not provided directly, then RR can be derived as: 
 [1] If QTcB is machine read & QTcF is not provided, then: $RR = \left[\left(\frac{QT}{QTcB} \right)^2 \right] * 1000$ [2] If QTcF is machine read and QTcB is not provided, then: $RR = \left[\left(\frac{QT}{QTcF} \right)^3 \right] * 1000$ If ECGs are manually read, the RR value preceding the measurement QT interval should be a collected value, THEN do not derive.
Corrected QT Intervals

When not entered directly in the eCRF, corrected QT intervals by Bazett's (QTcB) and Fredericia's (QTcF) formulas will be calculated, in msec, depending on the availability of other measurements.
IF RR interval (msec) is provided then missing QTcB and/or QTcF will be derived as:
$QTcB = \frac{QT}{\sqrt{\frac{RR}{1000}}}$ $QTcF = \frac{QT}{\sqrt[3]{\frac{RR}{1000}}}$

Worst Case Rules
Worst case finding based on the interpretation and the clinical significance:

 Count the participant as 'ABNORMAL' and 'CLINICALLY SIGNIFICANT', if any of the findings are 'ABNORMAL' and 'CLINICALLY SIGNIFICANT' during the time period/Post-Baseline. Else count the participant as 'ABNORMAL' and 'NOT CLINICALLY SIGNIFICANT', if any of the findings are 'ABNORMAL' and 'NOT CLINICALLY SIGNIFICANT' and none of the findings are 'ABNORMAL' and 'CLINICALLY SIGNIFICANT' during the time period/Post-Baseline. Else count the participant as 'NORMAL' if there is a finding of 'NORMAL' and none of the findings are 'ABNORMAL' during the time period/Post-Baseline. Otherwise, do not count the participant during the time period/Post-Baseline, i.e. little n will reflect that the subject is not counted in the time period/Post-Baseline.

Laboratory Parameters

- All BLQ values will be imputed with $\frac{1}{2}$ LLOQ.
- All ALQ values will be imputed with the ALQ + [smallest positive number with the same number of decimal places as the ALQ is reported with]
- Values reported as $< x$ are assumed to have an LLOQ of x.
- Values reported as $> x$ are assumed to have an ALQ of x.

12.7. Appendix 7: Reporting Standards for Missing Data

12.7.1. Premature Withdrawals

Element	Reporting Detail
General	
 • A participant is considered to have completed the study if they have completed all phases and periods of the study including the last visit. • Withdrawn participants may be replaced (as detailed in Section 2.3) in the study in order to ensure sufficient participants complete the study. Replacement participants will be assigned to the same treatment sequence as the participant they are replacing, at the discretion of the Sponsor and in consultation with the Principal Investigator. • All available data from participants who were withdrawn from the study will be listed and all available planned data will be included in summary tables and figures, unless otherwise specified. • Withdrawal visits will be slotted as per Appendix 3: Assessment Windows or will be summarised as withdrawal visits.

12.7.2. Handling of Missing Data

Element	Reporting Detail
General	
 • Missing data occurs when any requested data is not provided, leading to blank fields on the collection instrument: 
 ○ These data will be indicated by the use of a “blank” in subject listing displays. Unless all data for a specific visit are missing in which case the data is excluded from the table. ○ Answers such as “Not applicable” and “Not evaluable” are not considered to be missing data and should be displayed as such.
MMRM Analysis	
 • All the available assessments taken at scheduled visits will be included in the repeated measures models in which missing data are not explicitly imputed but the correlation between visits for all participants is used to adjust the estimate of treatment effect considering any missing data.

12.7.2.1. Handling of Missing and Partial Dates

Element	Reporting Detail
General	
 • Partial dates will be displayed as captured in participant listing displays.
Adverse Events	
 • The eCRF allows for the possibility of partial dates (i.e., only month and year) to be recorded for AE start and end dates; that is, the day of the month may be missing. In such a case, the following conventions will be applied for calculating the time to onset and the duration of the event: 
 ○ Missing Start Day: First of the month will be used unless this is before the start date of study treatment; in this case the study treatment start date will be used and hence the event is considered On-treatment as per Appendix 4: Study Phases and Treatment Emergent Adverse Events. ○ Missing Stop Day: Last day of the month will be used, unless this is after the stop date of study treatment; in this case the study treatment stop date will be used. • Completely missing start or end dates will remain missing, with no imputation applied. Consequently, time to onset and duration of such events will be missing.

Element	Reporting Detail
Concomitant Medications/ Medical History	
Partial dates for any concomitant medications recorded in the CRF will be imputed using the following convention:
If the partial date is a start date, a '01' will be used for the day and 'Jan' will be used for the monthIf the partial date is a stop date, a '28/29/30/31' will be used for the day (dependent on the month and year) and 'Dec' will be used for the month.The recorded partial date will be displayed in listings.

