5. CONSIDERATIONS FOR DATA ANALYSES AND DATA HANDLING CONVENTIONS

5.1. Study Treatment & Sub-group Display Descriptors

Treatment Group Descriptions			
RandAll NG		Data Displays for Reporting	
Code	Description	Description	Order in TLF
A	3 mg/kg IV GSK3858279	GSK3858279	2
P	Placebo	Placebo	1

Treatment comparisons will be displayed as follows using the descriptors as specified:

1. GSK3858279 vs Placebo

For treatment sequence displays:

Treatment Group Descriptions			
RandAll NG		Data Displays for Reporting	
Code	Description	Description	Order in TLF
A/P/P	3 mg/kg IV GSK3858279 – Placebo – Placebo	GSK3858279-Placebo-Placebo	2
P/A/A	Placebo – 3 mg/kg IV GSK3858279 – 3 mg/kg IV GSK3858279	Placebo- GSK3858279- GSK3858279	1
		Total	3

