12.4. Appendix 4: Study Phases and Treatment Emergent Adverse Events

12.4.1. Study Phases

Assessments and events will be classified according to the time of occurrence relative to the start date of the study treatment.

Study Phase	Definition
Pre-Treatment	Date/Time < Study Treatment Dose Date/Time (Period 1)
On-Treatment	Study Treatment Dose Date/Time (Period 1) ≤ Date/Time

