12.6. Appendix 6: Derived and Transformed Data

12.6.1. General

Multiple Measurements at One Analysis Time Point	

 Mean of the measurements will be calculated and used in any derivation of summary statistics but if listed, all data will be presented. Participants having both High and Low values for Normal Ranges at any post-baseline visit for safety parameters will be counted in both the High and Low categories of “Any visit post-baseline” row of related summary tables. This will also be applicable to relevant Potential Clinical Importance summary tables. 	
Study Period	

 The start date of Period [1/2/3] is the dosing Day 1 date for that period. The end date of Period [1/2] is the Day -1 date for the subsequent period. The end date for Period 3 and Period[1/2] if no subsequent period follows, will be the final follow up visit date, or if applicable, study withdrawal date, whichever date is earlier. 	
Study Day / Period Day	

 Study day is derived with respect to the very first dose date (Period 1): 
 Ref Date = Missing → Study Day = Missing Ref Date < Dose Date → Study Day = Ref Date – Dose Date Ref Date ≥ Dose Date → Study Day = Ref Date – (Dose Date) + 1 Period day is derived with respect to the dose date during that period: 
 Ref Date = Missing → Period Day = Missing Ref Date < Period Start Date → Period Day = Ref Date – Period Dose Start Date Ref Date ≥ Period Start Date → Period Day = Ref Date – (Period Dose Start Date) + 1 	

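### The adverse-event partial-date rules assume one continuous treatment; with three one-hour infusions they can put a stop date before a known start and can shift month-only Period 2 onsets to the other treatment.

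*SAP*

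**What the plan says.** SAP 12.7.2.1 covers adverse events for which only month and year are recorded.

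- **Missing start day:** "First of the month will be used unless this is before the start date of study treatment"; otherwise the treatment start date is used, and "hence the event is considered On-treatment as per" Appendix 4.
- **Missing stop day:** "Last day of the month will be used, unless this is after the stop date of study treatment"; otherwise the treatment stop date is used.
- **Stated purpose:** "the following conventions will be applied for calculating the time to onset and the duration of the event".

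The section does not say which infusion supplies the start or stop date. Elsewhere, SAP 12.4.1 defines the on-treatment phase as "Study Treatment Dose Date/Time (Period 1) ≤ Date/Time", with no upper limit. SAP 12.4.2 refers to the period definitions in SAP 12.6.1, which are dose by dose: "The start date of Period [1/2/3] is the dosing Day 1 date for that period" and "The end date of Period [1/2] is the Day -1 date for the subsequent period". SAP 5.1 lists two sequences, A/P/P (active, then "GSK3858279 – Placebo – Placebo" in full) and its mirror image P/A/A. The adverse-event tables in SAP 12.11.7 are mostly by period, and Table 3.03 has placebo and GSK3858279 columns.

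**The concern.** The rules suit a trial with one unbroken treatment interval. Here each treatment is a single one-hour infusion (Protocol 1.3.2), given three times at least four weeks apart (Protocol 4.1). Adverse events are collected until the follow-up visit (Protocol 8.2.1), which is 56±4 days after the last dose (Protocol 1.3.1).

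Two things follow. A stop date capped at an infusion date cannot accommodate events that begin or continue after that infusion. A start date floored only at the first dose can be placed before a later dose that preceded the event.

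Safety is a stated objective. Each participant receives both treatments, so the wrong side of the Period 1/2 boundary means the wrong treatment column. Columns are small: with at most 30 participants and 1:1 allocation in each period, a column holds about 15, and one participant is 1/15 = 6.7%. If the 5% threshold of Table 3.08 is applied by column, one moved event can cross it.

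**Working it through.** The plan states no figure here, so the rules were applied to dates.

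**Stop day**

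Take an event whose known start S is after the last infusion date D3, with only the stop month known. The last day of that month is on or after S, hence after D3, so the cap always applies and the imputed stop is D3 < S.

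Example: infusions on 17 May, 14 June and 12 July 2021; event starts 20 July; stop recorded as July 2021.
- Imputed stop: 31 July is after 12 July, so 12 July.
- Duration: (12 July − 20 July) + 1 = −8 + 1 = −7 days.
- A stop recorded as August 2021 would also become 12 July, contradicting the recorded month.

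The result depends on what the undefined stop date means. Each reading below assumes a known start day, a true stop two days after onset, and one event per day from first dose to 55 days after the last:

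| Reading of the stop date | Stop before start |
|---|---|
| Last infusion | 0% in Periods 1 and 2; 55/56 = 98% in Period 3; 39–49% overall |
| Infusion of the event's own period | 97–98% overall |
| Last dose + 90 days (the 18*5 term in SAP 12.6.2) | 0% |

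Under the first reading, an event that began before the last infusion and continued past it is not given a negative duration, but it is cut short.

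**Start day**

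The floor is taken as the Period 1 dose, through the on-treatment link to SAP 12.4.1. It is assumed that the imputed date also sets the period. Let a later dose fall on day m of a 30-day month, m uniform, with onsets uniform over the L days from that dose. Onsets in the dose month are imputed to day 1, before the dose, whenever m ≥ 2:

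share moved = (1/30) × Σ over m = 2..30 of min(1, (31 − m)/L)

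- L = 28: (1 + 1 + 13.5)/30 = 15.5/30 = 0.517
- L = 35: (435/35)/30 = 0.414
- L = 42: (435/42)/30 = 0.345
- Period 3, L = 56 because it runs to final follow-up (SAP 12.6.1): (435/56)/30 = 0.259

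Enumerating real calendar dates, with the first dose on each day of 2021, gives nearly the same shares:

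| Dose interval | Period 2 events moved to Period 1 | Period 3 events moved | Period 3 treatment changed |
|---|---|---|---|
| 28 days | 52.3% | 26.3% | 0.1% |
| 35 days | 42.1% | 26.3% | 0.0% |
| 42 days | 35.0% | 26.3% | 0.0% |

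Both listed sequences switch treatment between Periods 1 and 2 and repeat the same treatment in Period 3. Every Period 2 move therefore swaps treatment; a Period 3 move almost never does. Over all month-only starts, 21–26% change period and 10.5–13% change treatment.

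In the example, an event that began on 16 June and is recorded as June 2021 becomes 1 June: Period 1, the other treatment.

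**Would using that month's dose date be better?** Under the same assumptions it pulls Period 1 onsets forward into Period 2. The share is (1/30) × Σ over m = 2..30 of min(1, (m − 1)/28) = 15.5/30 = 0.517. The error is the same size in the opposite direction.

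**The case against.** The strongest reply is scope. SAP 12.7.2.1 offers the conventions for time to onset and duration, not for assigning period or treatment, and its text does not name Period 1. A reader might infer that the SAP instructs programmers to move these events to the other treatment; it does not say so. The inference rests on the on-treatment clause, on SAP 12.4.1, and on the absence of any other rule for placing a partial-date event. That stands as a limit on the start-day point, but the absence of a rule is itself a gap.

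Second, the treatment stop date is undefined, and the exposure formula in SAP 12.6.2 runs 90 days past the last dose. If that was meant, no stop precedes its start. Nothing in SAP 12.7.2.1 points there, and SAP 12.6.2 also records infusion stop times, so the infusion date is the more natural reading.

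Third, a reader might infer that every month-only stop after the last infusion yields a negative duration. That fails when the start day is also missing in the infusion month: in the example, start and stop both recorded as July 2021 become 1 and 12 July.

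Fourth, the practical exposure is limited. No adverse-event table title in SAP 12.11.7 mentions duration or time to onset, listings show the partial date as recorded, and this is a single-centre trial with repeated visits. All of this stands and keeps the point minor.

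**Conclusion.** The point holds as a low-priority defect. The stop-day rule fails at its own stated purpose on the natural reading: any event with a known start after the day of the last infusion and a month-only stop gets a stop before its start, and earlier events that continue past that infusion are shortened. Only a later meaning of the stop date, such as last dose plus 90 days, removes this.

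The start-day gap is conditional on the imputed date being used for period assignment. If so, 35–52% of month-only Period 2 events change treatment, depending on a dose interval of 42 down to 28 days. It would be tempting to apply 52% to Period 3 as well. That would require all Period 3 events to fall within 28 days of the dose, whereas Period 3 extends to final follow-up; the figure is about 26%, with treatment changing in 0.1% or fewer.

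All shares assume onsets spread evenly over time and apply only to events with a missing day. The documents give no frequency for these; few are expected, so the effect on the safety tables should be small.

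**What to change.** Amend SAP 12.7.2.1 in two places.

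1. **Stop day.** Impute to the last day of the recorded month, capped at study completion or withdrawal rather than the treatment stop date, and never earlier than the recorded or imputed start.
2. **Start day.** Where the recorded month contains a Period 2 or Period 3 dose, take the period from the visit or period at which the event was recorded and from any known stop date. Apply a stated tie rule only if these do not settle it. Defaulting to that month's dose date is not a cure, since it misplaces a similar share the other way. One candidate tie rule already has a precedent in the SAP: the programming note to Table 3.23 puts liver events reported in washout under the last treatment received.

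The cost is a few sentences and the matching derivation code. Whether the case report form links each event to a visit or period needs checking, because the documents do not show it. A footnote giving the number of events placed by the tie rule would let readers judge its effect.
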